## 4 Study Design

This is a prospective, open label post market study to evaluate the long-term safety and effectiveness of PAE using Embosphere Microspheres. Up to 500 patients with LUTS due to BPH will be enrolled in this single arm post market study. All patients at sites who meet eligibility criteria will be offered participation. Long term effectiveness of PAE on LUTS will be evaluated by IPSS score at baseline, 3 months, 12 months, and 24 months. Note: All subjects will be asked to complete the IPSS. However, study subjects who have an indwelling bladder catheter will not be required to complete the IPSS; the IPSS questions may not be relevant to subjects with an indwelling bladder catheter. Safety will be assessed by evaluating device and procedure-related adverse events at the same time points, plus at 4 weeks following embolization. Erectile function will be assessed at baseline and 12 months by SHIM score. Additional treatments for refractory or recurrent LUTS due to BPH post prostatic artery embolization will also be recorded.

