## 6.6 Additional Evaluations

Data will also be collected for additional evaluations that occur at any times outside of the above protocol-defined timepoints. If a patient receives any additional PAE procedures with Embosphere Microspheres, he will remain in the study, and the schedule for the follow-up evaluations will begin according to the date of the first PAE with Embosphere Microspheres procedure until the subject reaches a total of 24 months follow-up. End of study at 24 months is calculated on subject's first PAE procedure and not any additional PAE procedures.

Table 1. Schedule of Events

Table 1 identifies the Schedule of Events below. Follow-up may occur in the form of an in-person office visit, phone call, or mail. Information may be collected by email or text if the patient has documented that this is acceptable.

	Baseline	PAE Procedure	Visit 1	Visit 2	Visit 3	Visit 4	Unscheduled Visits
			4 Weeks (±1 week/± 7 days)	3 Months (±2 weeks/± 14 days)	12 Months (±8 weeks/±56 days)	24 Months (±8 weeks/±56 days)	
Informed Consent	X						
Demographics	X						
Prostate Size Assessment	X 						
Prior BPH Procedures	X						
Prostate Biopsy	X 						X 
Prostate Specific Antigen (PSA)	X 		X		X		X 
PAE Procedure		X					
Sexual Health Inventory for Men (SHIM)	X 				X		
International Prostate Symptom Score (IPSS)	X 			X	X	X	X 

	Baseline	PAE Procedure	Visit 1	Visit 2	Visit 3	Visit 4	Unscheduled Visits
			4 Weeks (±1 week/± 7 days)	3 Months (±2 weeks/± 14 days)	12 Months (±8 weeks/±56 days)	24 Months (±8 weeks/±56 days)	
BPH related medications (5α-Reductase inhibitors, α-blockers, etc.)	X		X	X	X	X	X 
Device or Procedure-Related Adverse Events		X	X	X	X	X	X 
Urinary Evaluations (Indwelling urinary catheter use, Qmax and PVR)	X 			X	X	X	X 
Additional prostate procedures and/or imaging			X	X	X	X	X 

 Prostate biopsy within 12 months of PAE procedure

 Baseline SHIM to occur within 4 weeks of PAE procedure

 Baseline IPSS to occur within 4 weeks of PAE procedure

 Within timeframe consistent with standard of care

 Unscheduled visits may include one or more of the identified evaluations

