#### **8.1.2 Secondary Endpoints**

The following are the secondary endpoints:

- IPSS measured at 3, 12, and 24 months post-baseline
- Device or Procedure-Related Adverse event rate at post-procedure, 3, 12, and 24 months
- Technical Success defined as the successful embolization of the treated prostate gland
- Frequency of indwelling bladder catheter removal post PAE at 3, 12, and 24 months
- Number of patients and types of treatment for refractory or recurrent LUTS due to BPH post PAE at 3, 12, and 24 months
- Change from baseline in Sexual Health Inventory for Men (SHIM) at 12 months post-PAE.

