### **8.5.1.2 Timing**

*Overall Timing:* Day 0 is the date of the procedure. Study Day will be calculated relative to the randomization as follows:

- Study Day = Assessment Date – Procedure Date

*Duration:* Duration variables will be calculated as follows:

- Duration Days = Start Date – End Date

A day is defined as 24 hours, from 0:00 to 23:59. 24:00 means 0:00 of the next day.

Each subject duration in the study will be based on the last study contact date, which is the latest date of all follow-up visits, assessments, adverse event onset or resolution, and study exit, including date of death.

*Visit Windows:* Unless otherwise specified, visit assessments will be analyzed for each analysis time point according to the study visit entered in the electronic Case Report Form (eCRF) to determine if the visit was within compliance.

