## 8.5.3 Analysis of the Secondary Endpoints

### 8.5.3.1 IPSS changes over time

The changes over time in the IPSS using the EAS will be modeled using a linear mixed model where country and patient will be considered a random effect. If there is evidence of non-linearity, a nonlinear mixed-effects model using a 3rd-degree

 Tibshirani, Robert (1996). "Regression Shrinkage and Selection via the lasso". Journal of the Royal Statistical Society. Series B (methodological). Wiley. 58 (1): 267–88. JSTOR 2346178.

polynomial will be implemented. The predicted curve and 95% confidence interval will be reported. Missing data will not be imputed.

Sensitivity analyses using complete cases and missing values replaced with an age-specific average will be performed.

A multivariate linear model will be developed to predict the IPSS changes over time. Univariate analysis will be performed analyses for all the baseline characteristics. Based on those results combined with clinical judgment, a final set of baseline characteristics will be created for use in the multivariate model. The LASSO regression analysis method will be used to perform variable selection and regularization.

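### The cubic time curve planned for IPSS rests on four scheduled times with no stated time scale, and in raw months it can show a relapse between 12 and 24 months that did not happen.

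*Combined protocol and SAP*

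**What the plan says.** Section 4 schedules the "IPSS score at baseline, 3 months, 12 months, and 24 months". Section 8.1.2 defines the secondary endpoint by visit: "IPSS measured at 3, 12, and 24 months post-baseline".

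Section 8.5.3.1 sets the analysis: "The changes over time in the IPSS using the EAS will be modeled using a linear mixed model", with country and patient as random effects. It continues: "If there is evidence of non-linearity, a nonlinear mixed-effects model using a 3rd-degree" polynomial. The output is fixed: "The predicted curve and 95% confidence interval will be reported".

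The section does not say whether time is nominal or actual, in days or months, or transformed. It gives no criterion for non-linearity. It also leaves open whether the outcome is the score or the change from baseline.

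Section 8.5.1.2 points two ways and is not tied to this model. One rule is nominal: "visit assessments will be analyzed for each analysis time point according to the study visit entered". The other defines time from dates: "Day 0 is the date of the procedure. Study Day will be calculated relative to the randomization as follows", followed by a formula that subtracts the procedure date from the assessment date.

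Table 1 in section 6.6 allows IPSS off schedule ("Unscheduled visits may include one or more of the identified evaluations"), but none is planned.

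**The concern.** A cubic has four coefficients and there are four scheduled times. At nominal visits the model therefore reproduces the four visit means, and the polynomial alone dictates the shape between them. IPSS is expected to drop steeply in the first three months and then level off, and the visits are unequally spaced. In raw months a cubic can follow that pattern at the visits only by undershooting after month 3 and overshooting after month 12.

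The study's stated goal is long-term safety and effectiveness. A reported curve that rises between 12 and 24 months could be read as symptom recurrence in patients who stayed well. The confidence interval would not warn the reader, because it reflects sampling error and takes the cubic form as correct.

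**Working it through.** The documents give no figure for this curve, so there is none to reproduce.

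**Inputs.** Section 1 gives mean IPSS of 21.5 (SD 6.8) at baseline, 6.3 (SD 5.8) at 1–3 months and 6.2 (SD 5.8) at 9–16 months. I place the last two at months 3 and 12. No 24-month mean is given; I assume 6.2 (SD 5.8) and vary the mean. Section 8.3 allows 10% missing from 500, so n = 500 × 0.9 = 450.

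**Is the fallback triggered?** The least-squares line through the four means is 14.24 − 0.430 × month.

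| Month | Mean | Straight line |
|---|---|---|
| 0 | 21.5 | 14.2 |
| 3 | 6.3 | 13.0 |
| 12 | 6.2 | 9.1 |
| 24 | 6.2 | 3.9 |

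The line misses month 3 by 6.7 points. On visit number, square-root months or log(month+1) it still predicts 11.9 to 12.4 there. Any reasonable check would find non-linearity.

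**The cubic in raw months, nominal visits.** The cubic through the four means is 21.5 − 6.9617m + 0.68428m² − 0.017532m³. Its derivative is zero at m = 6.94 (value 0.28) and m = 19.08 (value 16.00).

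**Why month 19 is wrong.** The fitted value at month 19 is a weighted sum of the four visit means:
- baseline: (16)(7)(−5) / [(−3)(−12)(−24)] = 0.648
- 3 months: (19)(7)(−5) / [(3)(−9)(−21)] = −1.173
- 12 months: (19)(16)(−5) / [(12)(9)(−12)] = 1.173
- 24 months: (19)(16)(7) / [(24)(21)(12)] = 0.352

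When the 3- and 12-month means agree, those two terms cancel. What remains is 0.65 of the pretreatment mean and 0.35 of the 24-month mean.

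**Confidence interval at month 19.** With uncorrelated visits, the variance is the sum of (weight² × SD²)/n = (19.4 + 46.3 + 46.3 + 4.2)/450 = 0.258, so SE = 0.508. The 95% interval is 16.0 ± 1.96 × 0.508 = 15.0 to 17.0. At n = 200 it is 14.5 to 17.5. With within-patient correlation 0.5 (assumed) it is 15.2 to 16.8 at n = 450.

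**Sensitivity of the false peak (raw months, nominal visits).**

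| Changed input | Peak |
|---|---|
| 24-month mean 4 / 8 / 10 / 12 | 15.2 / 16.7 / 17.5 / 18.3 |
| 3-month mean 8 / 10 / 12 / 14 | 14.0 / 11.7 / 9.3 / 7.0 |

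**Other time scales, flat scenario.** The lowest and highest values after month 3 are 5.28 and 7.15 (visit number), 5.34 and 6.85 (square-root months), and 5.65 and 6.41 (log(month+1)).

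**Actual dates.** Mixed models were simulated with n = 450, baseline at day 0, patient SD 3.5, and residual SD 5.8 at baseline and 4.6 at follow-up (all SDs assumed). Eight runs were made for each visit pattern:

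| Visit pattern | Month 19 | Fitted 12-month mean too low by |
|---|---|---|
| Even over the windows | 11.4 to 12.5 | 1.0 to 1.4 |
| Clustered near target | 13.2 to 14.9 | 0.4 to 0.6 |

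**If the outcome is change from baseline at the three follow-up visits only.** At nominal times the cubic design matrix has rank 3 for four coefficients, so the model cannot be estimated. If baseline enters as a change of 0, the curve is the same, shifted down by 21.5.

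**The case against.** The strongest reply is that the SAP never specifies raw months at nominal visits, and that 16.0 is the worst of the scales tried. That is true, and on three other scales the problem nearly vanishes. But the size of the artefact then depends on a choice the plan leaves open. The only numeric time variable it defines, Study Day, is untransformed.

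A continuous curve would also sit more naturally on actual dates, where month 19 is nearer 12 to 14 than 16. Section 6.1 allows the baseline IPSS up to four weeks before the procedure; spreading baseline over that window gives about 11 to 13. These are fair reductions in size, but the false rise remains.

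The intervals above omit the planned country effect. With four equally weighted countries and an assumed between-country SD of 1 or 2, the interval at n = 450 widens to 14.6 to 17.4 or 13.8 to 18.2. It still excludes 6.2.

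The means are borrowed from a cohort that included 54 men with indwelling catheters, whereas the evaluable set excludes men catheterised at the end of the procedure. The 24-month value is assumed, and a slower early response shrinks the peak. All of this stands as a limit on the magnitude.

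Finally, no endpoint or decision uses month 7 or month 19, and such a curve would look odd beside tabulated visit means. That limits the harm. It is not a reason to publish the curve.

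**Conclusion.** The concern holds. On the protocol's own background means the cubic fallback is very likely to be used. In raw months it creates a false rise to about 16 at nominal visits, or roughly 11 to 15 with actual dates, where the assumed true level is 6.2. The size rests on the borrowed means, the assumed 24-month mean and the assumed SDs. The direction follows from a steep early drop, a plateau and unequally spaced visits.

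The consequence is bounded. The analysis is secondary and has no decision rule, and the primary analysis in section 8.5.2 is untouched. At nominal times the estimates at the visits, including 24 months, are exact. The change should be made, but the trial's main result does not depend on it.

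**What to change.** In section 8.5.3.1:

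- Enter visit as a categorical factor (baseline, 3, 12, 24 months) in the planned mixed model and keep the random effects of country and patient.
- Report visit-specific means with 95% confidence intervals in place of the polynomial curve. This matches the endpoint in section 8.1.2.
- State whether the outcome is the IPSS score or its change from baseline.
- If a curve is wanted, use a piecewise-linear form with knots at 3 and 12 months. At nominal times it passes through every visit mean. With actual dates it gave 6.0 to 6.4 at month 19 in the simulation, but ran about 0.2 to 0.6 points low at month 3; categorical visit avoids that.
- If the cubic is kept, fix the time scale in advance. On log(month+1) the false peak in the flat scenario is 6.4 instead of 16.0. The curve would still be saturated at nominal times and would still dip between months 3 and 12, to 6.0 if the 24-month mean is 4 and to 4.6 if it is 12.

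The cost is SAP wording only, with the same data and software and no effect on patients or sites. What is lost is a smooth curve between visits, for which no IPSS measurements are planned.

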### **8.5.3.2 Device or Procedure-Related Adverse event rate at post-procedure, 3, 12, and 24 months**

Treatment-related adverse event rates will be discussed in section 9.3.

### **8.5.3.3 Technical Success**

Technical success will be reported separately as the proportion and the 95% confidence interval of patients in FAS that achieve technical success.

### **8.5.3.4 Successful embolization**

For each of the following, the proportion and the 95% confidence interval of patients in FAS will be reported:

- Successful embolization of the right prostate gland during the index procedure
- Successful embolization of the left prostate gland during the index procedure
- Successful embolization of both left and right prostate glands during the index procedure

### **8.5.3.5 Number of patients and types of treatment for refractory or recurrent LUTS due to BPH post-PAE**

The types of treatment and the number of patients that received that treatment for refractory or recurrent LUTS due to BPH post-PAE will be reported at 3, 12, and 24 months, and overall will be reported using the FAS.

### **8.5.3.6 Sexual Health Inventory for Men over time**

The mean and 95% confidence interval of the change from baseline in the Sexual Health Inventory for Men (SHIM) will be reported using the EAS at 12 months post-PAE.

### **8.5.3.7 Removal of In-dwelling catheter**

Using the FAS, for patients who had an indwelling catheter during the procedure, the proportion of indwelling bladder catheter (IBC) removal post-PAE will be reported at 3 and 12 months PAE.

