## 7 Patient Completion and Discontinuation

Patients will be informed that they have the right to withdraw from the study at any time for any reason, without prejudice to their medical care. The investigator also has the right to withdraw patients from the study for any reason. If a patient is withdrawn or discontinued from the study, the reason for withdrawal from the study will be recorded on the end of study form. These subjects will not be replaced.

A subject will be considered lost to follow-up if he fails to return for more than one scheduled visit and is unable to be contacted by the study site staff.

The following actions must be taken if a subject fails to return for a required study visit:

- The site will attempt to contact the subject and reschedule the missed visit within the allowable visit timeline and counsel the subject on the importance of maintaining the assigned visit schedule and ascertain if the subject wishes to and/or should continue in the study
- Before a subject is deemed lost to follow-up, the Investigator(s) or designees will make every effort to regain contact with the subject (where possible, 3 telephone calls and, if necessary, a certified letter to the subject's last known mailing address or local equivalent methods). These contact attempts must be documented

- Should the subject continue to be unreachable, he or she will be considered to have withdrawn from the study with a primary reason of lost to follow-up

If a patient receives any non-PAE BPH procedure other than biopsy after his study PAE he will be automatically discontinued from the study, and follow-up data will no longer be collected. BPH procedures that will automatically discontinue the patient include but are not limited to TURP, Urolift, microwave ablation, aquablation, laser therapy and non-Embosphere Microspheres PAE.

Patients requiring multiple PAE procedures:

- If a patient receives an additional PAE procedure with Embosphere Microspheres after the initial treatment, he will remain in the study, and the schedule for the follow-up evaluations will begin according to the date of the first PAE with Embosphere Microspheres procedure until the subject reaches a total of 24 months follow-up. End of study will be calculated based on first PAE procedure for 24 months.

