### **8.5.1.5 Missing Data**

All attempts will be made to limit the amount of missing data. For all analyses of the primary endpoints, the number of observations available will be reported so the reader can assess the impact of missing data. For all clinical endpoints except for the patient-reported outcome measurements, an adjustment to the denominator will be made based on the amount of evaluable data. For each visit (or reporting time point), the event rate will be calculated as the number of subjects with certain event terms over the number of evaluable subjects. The evaluable subjects at each reporting time point include all subjects who are enrolled and

- 1) had an event within (on or before) the reporting cutoff days, or

- 2) had a follow-up at or after the lower limit of the reporting window, or
- 3) the withdrawal consent date/recorded lost-to-follow-up date at or after the lower limit of the reporting window.

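### The evaluability rule in 8.5.1.5 drops men who have another BPH procedure while still catheterised, so the catheter-removal rate in 8.5.3.7 would be biased upward; 8.5.3.7 should say how they count

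*Combined protocol and SAP*

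**What the plan says.** Four places bear on this endpoint.

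- **Section 8.1.2** lists the endpoint as "Frequency of indwelling bladder catheter removal post PAE at 3, 12, and 24 months".
- **Section 8.5.3.7** sets the population: "Using the FAS, for patients who had an indwelling catheter during the procedure". For these men it says that "the proportion of indwelling bladder catheter (IBC) removal post-PAE will be reported at 3 and 12 months PAE". It does not say how a man who has left the study is counted.
- **Section 7** deals with a man who has a BPH procedure other than PAE or biopsy: "he will be automatically discontinued from the study, and follow-up data will no longer be collected". On the triggering procedures it says "BPH procedures that will automatically discontinue the patient include but are not limited to TURP", and it lists several others.
- **Section 8.5.1.5** says: "For all clinical endpoints except for the patient-reported outcome measurements, an adjustment to the denominator will be made". A subject is evaluable at a time point by one of three routes: he had the event by the cutoff; he "had a follow-up at or after the lower limit of the reporting window"; or his consent withdrawal or recorded loss to follow-up is dated at or after that same lower limit.

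Section 8.5.3.5 reports additional treatments for refractory or recurrent LUTS separately, in the FAS. Nothing there feeds into the removal proportion.

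**The concern.** A rule of the 8.5.1.5 kind suits adverse events. The counted event is unfavourable, and a man who leaves early without one has not been observed long enough to be called event-free. For catheter removal the event is the favourable one. One of the ways out of the study, another BPH procedure while still catheterised, shows that PAE had not freed the man of his catheter by then. His outcome up to that date is known, yet the rule treats him as not evaluable.

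The matter is not trivial for this subgroup. Section 4 does not require the IPSS from men with an indwelling catheter, and section 8.4.2 leaves men with a catheter at the end of the procedure out of the EAS. Catheter removal is therefore one of the few effectiveness results that covers them, together with the section 3.2 objective on IPSS and QoL after the catheter is discontinued. Under the 8.5.1.5 rule, for a given number of removals, the rate looks better the more men are operated on early.

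**Working it through.** The documents state no removal rate, denominator or precision target for this endpoint, so there is no planned figure to reproduce. The check applies the rule to the man in question and then shows what it does to the proportion.

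**Step 1. When each window opens** (Table 1, taking 3 months as 91 days and 12 months as 365 days)
- 3 months: 91 − 14 = day 77
- 12 months: 365 − 56 = day 309

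**Step 2. A man still catheterised who has, for example, TURP before that day**
- Route 1 (event by the cutoff): no, his catheter has not been removed.
- Route 2 (follow-up at or after the lower limit): no, section 7 stopped his data collection.
- Route 3 (consent withdrawal or loss to follow-up at or after the lower limit): no. Discontinuation for a procedure is not named, and if it were treated as a withdrawal, its date would be too early.

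He drops out. By contrast, a man whose catheter came out by the cutoff qualifies by route 1 however early he leaves. A man with follow-up at or after the lower limit stays in and counts as not removed.

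**Step 3. Effect on the proportion**

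Let C be the catheterised FAS men, R those with a recorded removal, and d those discontinued for a procedure before the window with no removal. Considering only these exits:
- 8.5.1.5 rule: R/(C − d)
- all catheterised FAS men: R/C
- difference: R·d / [C(C − d)], which is positive whenever R and d are both above zero

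The direction therefore depends on no assumed number.

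**Step 4. Illustration of size**

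Section 1 reports 54 of 286 men in the earlier cohort with indwelling catheters: 54/286 = 18.9%. Section 8.3 plans up to 500 men. If the share is the same here, C = 0.189 × 500 ≈ 94. Assume R = 70, which leaves 94 − 70 = 24 failures. R and d are assumptions; neither is in the documents.
- All FAS men: 70/94 = 74.5%
- d = 5 (21% of the failures): 70/89 = 78.7%, or +4.2 points
- d = 12 (half of the failures): 70/82 = 85.4%, or +10.9 points

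Over a wider assumed range, with C = 94:

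| R (R/C) | Failures | A quarter dropped | Half dropped |
|---|---|---|---|
| 56 (59.6%) | 38 | 56/84 = 66.7% (+7.1) | 56/75 = 74.7% (+15.1) |
| 66 (70.2%) | 28 | 66/87 = 75.9% (+5.6) | 66/80 = 82.5% (+12.3) |
| 75 (79.8%) | 19 | 75/89 = 84.3% (+4.5) | 75/84 = 89.3% (+9.5) |
| 85 (90.4%) | 9 | 85/92 = 92.4% (+2.0) | 85/90 = 94.4% (+4.0) |

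In the limit where every failure is operated on before the window, the rule gives R/R = 100% whatever the true rate.

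**The case against.** The strongest reply is that 8.5.3.7 already fixes its own denominator. It names the FAS, which under 8.4.1 excludes only men who withdrew consent before the index procedure. Section 8.5.1 makes its general principles, including 8.5.1.5, subject to anything specified otherwise. On that reading the operated man stays in as not removed and there is no bias. This is a fair reading, but 8.5.1.5 claims every clinical endpoint that is not patient-reported, and 8.5.3.7 claims no exemption. The two readings give different rates, and the plan does not choose between them.

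Three stronger readings are tempting and are not supported.
- A reader might infer that the excluded men are precisely the treatment failures. They are not: early deaths, consent withdrawals and losses without removal drop out too, and a man operated on after follow-up inside the window stays in.
- A reader might infer that surgery turns failures into successes. Section 7 ends data collection, so a removal after surgery should not be recorded. Only a removal around the time of the procedure could be recorded and counted, because 8.5.3.7 does not require that PAE brought it about.
- A reader might infer a large bias of known size. A gain near 19 points, 70/75 = 93.3% against 74.5%, needs 19 of the 24 assumed failures (79%) to be operated on while catheterised before the window. Nothing in the documents supports that rate.

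It is also true that this is a descriptive secondary proportion in a single-arm study, that 8.5.1.7 has patient numbers shown with percentages, and that 8.5.3.5 shows additional treatments. That limits the harm. It does not correct the proportion, because 8.5.3.5 is not split by catheter status.

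**Conclusion.** The point holds in this form. As 8.5.1.5 is written, men discontinued under section 7 for another BPH procedure before the window, with the catheter never removed, leave the denominator of the removal rate while all recorded removals stay in. The effect of losing these men is upward whenever any exist, and no other section corrects it. It rests on 8.5.1.5 governing the endpoint. If 8.5.3.7 is meant to override it, the defect is that the plan does not say so.

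The size cannot be derived from the documents. Under the assumptions shown (94 catheterised men, 70 removals), dropping 5 to 12 of the 24 failures adds about 4 to 11 points. It would be close to zero if few men are operated on before the window opens. The change is worth making before the analysis, since it affects how the result for men in retention is read and costs almost nothing.

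**What to change.** Add to 8.5.3.7, in substance:

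- The 8.5.1.5 evaluability rule does not remove men discontinued under section 7 for another BPH procedure. They stay in the denominator.
- Of these men, those with no catheter removal before that procedure count as not removed.
- A removal at or after that procedure is not counted as a removal post-PAE.
- A man whose catheter came out after PAE and before any later procedure remains a removal.

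The last line matters. A composite of catheter-free and no other BPH procedure would report such a man as not removed, which would be untrue and would change the endpoint listed in 8.1.2. While the section is open, its time points should be reconciled with 8.1.2, which also lists 24 months.

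The cost is SAP wording only, with no change to the discontinuation rule or to care. Catheter changes and additional prostate procedures are collected at the follow-up visits (6.3 and 6.4), the reason for discontinuation goes on the end of study form (section 7), and 8.5.1.2 uses the study exit date. Section 7 does not itself mention the procedure date, so it is worth confirming that the eCRF captures it. The reported rate will be somewhat less favourable than under 8.5.1.5.
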